## 1 Introduction

The present statistical analysis plan is prepared for the multi-site Hepatitis C Real Option (HERO) study sponsored by PCORI (HPC-1503-28122; Clinical Trial Registration #: NCT02824640). The HERO is a pragmatic randomized clinical trial designed primarily to test difference in sustained viral response (SVR) outcome among people who inject drugs between two models of care: directly observed therapy (DOT) vs. patient navigation (PN). This statistical analysis intends to maximize transparency and reproducibility of the statistical analysis results and minimize potential biases due to indication of statistical analysis results. To this end, this plan is prepared and approved by the entire HERO study investigator team prior to the completion of main outcome data collection and cleaning which is anticipated to be accomplished by April 2020. This plan primarily focuses on the comparative analysis of SVR outcome after 12 week-long Hepatitis C treatment period with direct-acting antiviral medications. Plans for analysis of several secondary outcomes are also addressed.

## 2 Independent Parallel Analysis

To ensure reproducibility of statistical analysis results, two independent statisticians, one at University of New Mexico (UNM) and another at Clemson, will comply as closely as possible with the analytical plans detailed herein, which are reviewed and approved by the HERO investigators. They will analyze the primary outcome, SVR, independently and in a parallel manner, and compare their results. If their results are substantially different beyond a tolerable variation, then the two statisticians will examine each other's analytic strategy and software codes to reach a consensus. Final results will be reported upon agreement of the two statisticians. Investigators will not be involved in this process, and more importantly, data analysis will not be guided or influenced by the indications of results. Each aspect of data analysis such as cleaning, analysis, and output will be logged and archived for review.

## 3 Definitions of Study Analytic Samples

All study participants must meet the screening inclusion and exclusion criteria AND sign the consent form. These participants are defined as enrolled participants/sample. From these enrolled participants, the analytic sample for all statistical analysis will be defined in the following three categories:

### 3.1 Primary analytic sample

This primary analytic sample includes the enrolled study participants who were *randomized and initiated* treatments. This sample is referred to as the *modified* intention-to-treat (mITT) analytic sample. The participants who initiated treatment will consist of those who had intake of at least one dose of the medication after randomization.

### 3.2 Secondary analytic sample

This secondary analytic sample includes all enrolled study participants who were *randomized*. This sample is referred to as the intention-to-treat (ITT) analytic sample.

### 3.3 Per protocol analytic sample

This per protocol (PP) analytic sample includes the enrolled study participants who 1) were randomized; 2) initiated treatment; 3) complied with the randomly assigned models of care without cross over any time during the 12-week treatment; and 4) had SVR outcome data (yes vs. no). This sample is referred to as the per-protocol (PP) analytic sample. The PP sample will be a subset of the mITT sample which is in turn a subset of the ITT sample.

The intention-to-treat principle reflects the principle that once the intervention was randomly assigned to a participant, the participant's intervention assignment will not change in the analysis even if s/he crossed over the other intervention during the trial period or did not complete intervention activities. The application of this ITT principle reflects the real-world goal of the HERO study which is to treat all PWID with HCV (i.e., all randomized individuals).

However, as the HERO study was designed as of a pragmatic randomized clinical trial (RCT), the ITT sample will not be used as the primary analytic sample because the outcomes are defined conditions on the initiation. Furthermore, the primary (SVR) and several of the other secondary outcomes (treatment completion, adherence) are only relevant among those who initiated treatment.

**All statistical analyses proposed in the present SAP will be repeated for each analytic sample.** Comparison across the three analytic samples will be compared to assess internal or external validities or limitations of the study findings. In particular, analysis of the secondary ITT sample will provide estimates of milestones along the HCV cascade of care by study arm and in the full sample. All statistical analyses will be conducted using SAS v9.4 and R 3.5 or higher, and a two-tailed significance level of 0.05 will be applied to all testing and confidence intervals.

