### 5.2 SVR determination process

SVR will be determined for each participant in the ITT sample, and thus for the mITT and PP samples as well. First, the time window for relevant viral load data for determination of SVR is set at between post-EOT (end of treatment) 10 week (or 70 days) and post-EOT 1 year (or 365 days). This time frame is further divided into two windows: the primary time window (post-EOT 70 days to 98 days) and the secondary time window (post-EOT 99 days to 365 days) (Figure 1). SVR status will be declared based on viremia data collected from the medical chart reviews or bio-repository data and classified into the following three categories: Success, Failure, and Undetermined. Detailed algorithm for the SVR determination process within the primary and secondary time windows is described in Figure 2.

Figure 1. Hero Study Post-EOT Timeline for SVR Determination

[figure not shown]
[figure not shown]

Figure 2. SVR Determination Process

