### 5.3 Handling undetermined/missing SVR data for primary analysis

#### 5.3.1 mITT analysis

- Primary approach: The undetermined SVR will be treated as SVR failure.
- Secondary approach: The undetermined SVR imputed by a fully specific conditional specification multiple imputation method. This imputation will be made stratified by the study arm. In each arm, overall adherence and the total duration of treatment will be used as predictors of the imputation model. Of note, the imputation will NOT be applied to undetermined SVR due to death; in this secondary approach, deaths will still be treated as SVR failure.

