#### 5.3.3 Per-protocol analysis

The missing SVR will be excluded by the definition of per-protocol sample. Therefore, the analysis will use completely observed SVR, successful or failed, for this analysis without necessity of imputation.

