### 8.3 Treatment Completion

The primary treatment completion outcome (100% completion) will be declared “yes” if a participant went through at least 84 days of treatment from his/her start treatment date to end treatment date regardless of adherence to the medications. By this definition, there will be no undetermined treatment completion status in any of the three analytic samples. The secondary treatment completion outcome (80% completion) will be determined based on whether a patient was treated for 68 days at least, which is 80% of the prescribed 84 treatment days, i.e., whether or not the length between the start and end dates (both inclusive) are greater than or equal to 68 days. The third treatment completion outcome will be the number of treatment days within the 84-day window on a continuous scale. Comparisons of median treatment days, third completion outcome, will be conducted as a secondary analysis.

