### 8.3.2 Statistical Model

All statistical procedures and models applied to the analysis of SVR detailed above will also be applied except for the missing data imputation which is unnecessary. All of ITT, mITT, and PP samples will be analyzed.

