### 8.4.2 Statistical Model

Mixed-effects linear model with the study as the primary predictor will be applied to the analysis of the blister-pack adherence data adjusting for the randomization stratification variables: sites, clinic types and cirrhosis status. This analysis will be applied to mITT and PP sample but not to ITT sample.

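### The per-protocol set requires an SVR result even for completion and adherence, which do not need one, so those supporting comparisons can be biased in an unknown direction

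*SAP*

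**What the plan says.** SAP 3.3 sets four conditions for the PP set: randomised, initiated, no crossover, and an SVR result. The last two read "without cross over any time during the 12-week treatment; and 4) had SVR outcome data (yes vs. no"). SAP 5.3.3 confirms the effect of the fourth: "The missing SVR will be excluded by the definition of per-protocol sample".

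The SVR result comes from viremia data in chart reviews or the bio-repository, taken "between post-EOT (end of treatment) 10 week (or 70 days) and post-EOT 1 year (or 365 days") (SAP 5.2).

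The same set is used for two outcomes other than SVR:

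- Completion (SAP 8.3.2): "All of ITT, mITT, and PP samples will be analyzed".
- Adherence (SAP 8.4.2): "This analysis will be applied to mITT and PP sample but not to ITT sample".

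Completion is computed from treatment start and end dates, and SAP 8.3 states that "there will be no undetermined treatment completion status in any of the three analytic samples". Adherence comes from electronic blister packs during treatment (SAP 8.4).

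The primary set has no SVR-data condition. It consists of randomised participants who took at least one dose: "This sample is referred to as the *modified* intention-to-treat (mITT) analytic sample" (SAP 3.1). For SVR in that set, the primary rule is "The undetermined SVR will be treated as SVR failure" (SAP 5.3.1).

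**The concern.** For the SVR analysis, condition 4 does what its authors intend: it gives an analysis of observed results. For completion and adherence it has no such purpose. Completion status is known for everyone, and whatever blister-pack data exist do not depend on a later viral load. The condition only removes people, and it does so on an event that follows the outcome being analysed.

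A link between stopping early and having no SVR result is plausible. Protocol 5.5 lists non-compliance with study requirements among the reasons for withdrawal. The imputation model in SAP 5.3.1 uses adherence and treatment duration to predict undetermined SVR. Neither proves the link, but both make it a reasonable worry.

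SAP 3.3 compares results across the three sets to judge the validity and limits of the findings. A reader would take a gap between mITT and PP on completion as a sign of crossover, the departure that condition 3 addresses. It could instead come from missing SVR tests.

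**Working it through.** **The plan's own figure.** Protocol 11.10 gives 80% (PN) against 89% (mDOT) completion as detectable, with OR 2.1. Inputs are 270 per arm after attrition, two-sided 0.05 and 80% power (Protocol 11.4). With a pooled-variance normal approximation, power at 270 per arm is 82.6%. Applying the 10% covariate R-squared that the plan states for SVR gives an effective 243 per arm, a detectable rate of 89.2% and OR 2.06, which rounds to 2.1. The figure reproduces. At exactly 80% and 89% the OR is (0.89/0.11)/(0.80/0.20) = 2.02. (SAP 8.3.3 gives 100 per arm, where power is only 42%. This conflicts with the 300 in SAP 5.5; it is a separate point and the 100 is not used here.)

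**Formula.** Let p be the true completion rate in an arm, c the share of completers with SVR data and n the share of non-completers with SVR data. Then:

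- PP completion rate = pc / [pc + (1 − p)n]
- PP OR = true OR × (c_DOT/c_PN) × (n_PN/n_DOT)

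The documents give neither c nor n. Both are assumptions, with c = 0.95 except where stated.

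**Equal loss in both arms.** With n = 0.5:

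- PN: 0.760/(0.760 + 0.100) = 88.4%
- DOT: 0.8455/(0.8455 + 0.055) = 93.9%

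Power is for the unadjusted Wald test of the log OR, starting from 300 per arm (SAP 5.5). For n = 0.5 the expected cell counts are 228 and 30 (PN) and 253.65 and 16.5 (DOT). The SE is √(1/228 + 1/30 + 1/253.65 + 1/16.5) = 0.320, and 0.704/0.320 − 1.96 = 0.24, so power is about 60%.

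| Non-completers lacking SVR | PN | DOT | Difference (points) | OR | Power | Overall lacking SVR, PN / DOT |
|---|---|---|---|---|---|---|
| Condition 4 not applied | 80.0% | 89.0% | 9.0 | 2.02 | 85% | – |
| 30% | 84.4% | 91.7% | 7.2 | 2.02 | 73% | 10% / 8% |
| 50% | 88.4% | 93.9% | 5.5 | 2.02 | 60% | 14% / 10% |
| 70% | 92.7% | 96.2% | 3.6 | 2.02 | 41% | 18% / 12% |

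**Unequal loss.**

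| Non-completers lacking SVR, DOT / PN | DOT | PN | Difference (points) | OR |
|---|---|---|---|---|
| 40% / 60% | 92.8% | 90.5% | 2.3 | 1.35 |
| 25% / 75% | 91.1% | 93.8% | −2.7 | 0.67 |
| 60% / 40% | 95.1% | 86.4% | 8.7 | 3.03 |
| 75% / 25% | 96.8% | 83.5% | 13.3 | 6.07 |

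If each arm loses 10% of its participants, all of them non-completers (c = 1), the rates are 0.89/0.90 = 98.9% and 0.80/0.90 = 88.9%. The difference is 10.0 points and the OR is (0.89/0.01)/(0.80/0.10) = 11.1. If the 10% loss is unrelated to completion, nothing changes: 9.0 points, OR 2.02.

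**Adherence.** This is a simulation with assumed means of 0.80 (DOT) and 0.75 (PN), SD 0.20, and values limited to 0–1. The probability of having SVR data rises with adherence. The true difference is 4.3 points. In the PP set it is:

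- 3.9 to 4.0 with the same selection rule in both arms
- 2.1 to 2.9 if PN loses more
- 5.0 to 5.5 if DOT loses more

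The share kept in an arm ranges from 55% to 96% across these runs.

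**The case against.** A reader might infer that condition 4 shrinks the arm difference by construction. The documents do not support that. SAP 8.3.2 carries over the SVR models, and SAP 5.4 reports an adjusted odds ratio. Selection that depends only on the outcome, equally in both arms, shifts the intercept of a logistic model and leaves the arm coefficient alone; hence 2.02 throughout the first table. Only the risk difference falls, and only because the base rates are high. At 40% against 30%, with half the non-completers and 5% of completers lost, it grows from 10 to 11 points. With unequal loss either measure can move either way.

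A reader might also infer that non-completers as a group drop out of the PP set. They need not. The window runs to day 365 and accepts chart or repository data, and follow-up visits are timed from treatment start (Protocol 8.6). Someone who stops at day 28 has a window of days 98 to 393, which contains the scheduled draws at weeks 24, 36 and 48 (days 168, 252 and 336). The algorithm in SAP Figure 2 was not available in the text reviewed, so how early failures are classified is not known here.

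The heavier loss scenarios are also open to challenge. Protocol 11.7 expects at most 10% attrition over the first 24 weeks. Of the three equal-loss cases, only the 30% one stays within that, and it leaves 7.2 of the 9.0 points. Finally, PP is a supporting set: mITT, and ITT for completion, keep these participants.

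All of this stands, and it limits the size and certainty of the problem. It does not supply a reason for condition 4 in these two analyses. An unchanged OR does not protect the test either: the people removed carry most of the information, so mITT and PP could differ in significance with no difference in effect. Nor does the OR argument cover adherence, which uses a linear mixed model, or treatment days, which are compared by medians (SAP 8.3).

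**Conclusion.** The point holds for supporting analyses only. Condition 4 is unnecessary for completion and adherence, and it selects participants on a post-treatment event. If missing SVR is related to non-completion, PP rates for both outcomes are too high. The arm comparison may then be biased, in a direction that the documents do not allow one to predict.

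Under equal loss with the assumed 50% and 5%, the completion OR is unchanged, the risk difference falls by 3.5 points and unadjusted power by about 25 percentage points. In the unequal-loss table the OR runs from 0.67 to 6.07. These sizes rest on assumed missingness rates. If missing SVR is unrelated to completion, there is no bias, only a smaller sample. The primary mITT analyses are not affected.

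**What to change.** Keep condition 4 for the SVR analysis only. For completion and adherence, define the PP set by conditions 1 to 3 (randomised, initiated, no crossover), and amend SAP 8.3.2 and 8.4.2 to refer to that set. Report the number with missing SVR by completion status and arm, so that a reader can see how far the SVR-based PP set differs.

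The cost is a few lines of SAP text, one more sample size to report and one small table. No new data are needed.

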## 4 Preliminary Data Analysis of Baseline Characteristics

### 4.1 Baseline Characteristics

We will consider the following baseline characteristic to characterize the HERO study participants [To be further determined]:

- Demographic Characteristics: Gender, Ethnicity, Race, Age, Education, Marital/ Cohabitation status, Potential Transportation Barrier, Housing status, Employment Status
- Clinical Characteristics: Clinical Setting (OTP or CHC), Cirrhosis, Anxiety Symptoms, Depression Symptoms, HIV/HCV coinfection, HCV-treatment history (Naïve or Experienced), HCV-related information (Genotype, HCV Viral Load), Other infectious

Diseases (HV, HBV, HAV), Medication for Opioid Use Disorder (buprenorphine, methadone)

- Behavior Characteristics: Hazardous alcohol drinking, Injection behaviors (duration, frequency, last drug injection), Substances injected (mixture of heroin and cocaine, mixture of methamphetamine and heroin, cocaine, methamphetamine, heroin, crack, fentanyl), Used drug type (amphetamine, benzodiazepine, , cocaine, opiate, methamphetamine, oxycodone, cannabis/THC)

Detailed information on the baseline characteristics including their definitions and classifications along with all data sources for each characteristic are displayed in Table 1. Briefly, for the baseline demographic factors, the data collected at enrollment visit (consent and demographic survey) will serve as the primary data sources. Data from the screening will serve as the secondary data sources. For the other clinical factors, the data at the screening (chart review 1), enrollment (Chart review 2), or baseline will serve as the primary data sources. If the data are not available at the primary sources, they will be replaced by the secondary data such as the Visit 1/Baseline (chart review 2) research visit data. For the behavior characteristics, the data at the screening or baseline will be used as the primary and only data sources. In short, the data collected at three different time point—screening, enrollment, and baseline/V1 visit (2 week period)—will serve as the primary, or secondary data sources depending on baseline characteristics in effort to minimize missing values.

Table 1. Baseline characteristics

Characteristic	Category	DOT (N=375)	PN (N=379)	Primary source	Secondary source
Gender 				E	S
	Female				
	Male				
	Transgender or Gender Non-conforming				
Age 				E	S
	Mean (SD)				
	Median (Q1, Q3)				
Race 				E	S
	White/Caucasian				
	Black/African American				
	Other				

Characteristic	Category	DOT (N=375)	PN (N=379)	Primary source	Secondary source
Latino/Hispanic Ethnicity 				E	S
Marital/cohabitation Status 				E	
	Single/Separated/Divorced/Widowed				
	Married/living together as married				
	Other				
Education 				E	
	Less than HS				
	HS diploma or GED				
	Some college or more				
Living situation 				E	
	Street/outdoors				
	Shelter				
	Someone else's apartment, house or room				
	Institution*				
	Own/rent apartment, house, or room				
	Other				
	Unstable housing*				
Availability of transportation 				E	
Yes					
Maybe, if I can get a ride					
Maybe, If public transportation is available					
No					
Employed with a regular job or informal work 				E	
Clinical Setting 				E	S
	OTP				
	CHC				
Any medication for OUD in the past 3 months 				B	

Characteristic	Category	DOT (N=375)	PN (N=379)	Primary source	Secondary source
	Buprenorphine				
	Methadone				
	None				
Depressive symptoms  (PHQ-9) [Mean (SD)]				B	
PHQ-9 Severity				B	
	Mild (<10)				
	Moderate (10-14)				
	Moderately severe/severe (>14)				
Anxiety symptoms (GAD-7)  [Mean (SD)]				B	
GAD-7 Severity 				B	
	Mild (<10)				
	Moderate (10-14)				
	Moderately severe/severe (>14)				
HCV Treatment History 				S	
Naive					
Experienced					
Cirrhosis 				CR1	CR2
Genotype (available) 				CR2	
Genotype				CR2	
	Type 1				
	Type 2				
	Type 3				
	Type 4				
	Mixed				
HCV viral load, IU/mL (available) 				CR1	CR2
HCV viral load, IU/mL				CR1	CR2
	Mean (SD)				
	Median (Q1,Q3)				

Characteristic	Category	DOT (N=375)	PN (N=379)	Primary source	Secondary source
HIV co-infection (available) 				CR2	
HIV co-infection (positive)				CR2	
HIV viral load (available)				CR2	
HIV viral load, <200copies/mL				CR2	
HIV viral load, ≥200copies/mL				CR2	
HBV surface antigen(available) 				CR2	
HBV surface antigen (positive)				CR2	
Hazardous alcohol use 				B	
Last drug injection (within 3 months from screening) 				S	
0-4 weeks					
5-8 weeks					
9-12 weeks					
Number of days injected drugs in the past 3 months 				B	
	Mean (SD)				
	Median (Q1, Q3)				
	Missing				
Times injecting drugs a day 				B	
	Mean (SD)				
	Median (Q1, Q3)				
	<3				
	≥3				
	missing				
Substances injected in the past 3 months 				B	
	Mixture of cocaine and heroin ^				

Characteristic	Category	DOT (N=375)	PN (N=379)	Primary source	Secondary source
	Mixture of methamphetamine and heroinB				
	HeroinC				
	MethamphetamineD				
	CocaineE				
	CrackF				
	FentanylG				
	Poly-substancesH				
Urine drug screen positive at baseline visit 				B	
	Amphetamine				
	Methamphetamine				
	Benzodiazepine				
	Cocaine				
	THC/Cannabis				
	Opiate				
	Oxycodone				
	Any drug				

Notes: S: Screening; E: Enrollment; B: Baseline; CR1 Chart review 1

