##### 8.1.1.a. Screening with Chart Reviews

Prior to conducting chart reviews of existing patients at the OTP and community clinics, sites will obtain a *Waiver of HIPAA authorization for screening/recruitment purposes*. Once this waiver is obtained, charts of potential participants will be reviewed to determine if the patient is eligible for participation.

- The following will be reviewed through Chart Review Part 1:
  - HCV Antibody (ever)
  - HCV viral load (ever)
  - HCV genotype/subtype (ever)
  - AST/ ALT and platelets in the past 12 months (for FIB-4 fibrosis estimation),
  - Imaging if available to rule out hepatocellular carcinoma if the participant has advance cirrhosis/fibrosis (abdominal ultrasound/CT scan with contrast, or MRI with contrast)
  - Confirm that the person has not previously received DAAs
  - **Document Study eligibility on CRF**

If subject is deemed eligible via “Chart Review Part 1”, then “Eligibility Screener” should be conducted.

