## 8.2 Visit 1: Baseline Visit

The baseline visit should occur within two weeks of enrollment and prior to treatment initiation. This visit will assess for several different factors including HCV clinical factors, potential mediating variables based on the information-motivation-behavioral (IMB) model, potential moderators, and additional psychosocial factors hypothesized to predict adherence, using the following research assistant administered instruments, in this order:

- Modified ASI – Baseline (assess drug use)
- Behavior risk assessment (assesses injection behaviors)
- AUDIT-C (assess alcohol use)
- Substance Use Treatment (assess past and present experience with treatment)
- PHQ-9 (assess depression)
- GAD-7 (assess anxiety)
- EQ-5D with added pain question (assess quality of life)
- Stigma scale
- Shame scale
- Health efficacy
- Medical Outcomes Social Support Scale

The baseline visit will also include specimen collection:

- Urine for POC drug screening
- Collect 20 mL of whole blood in EDTA tubes for archiving.

Additional services will be provided:

- Counseling on avoidance of HCV transmission and HIV infection will be conducted.
- Information on drug treatment and needle exchange programs will be provided, and other referrals as needed.

At this visit, after all baseline instruments have been administered, research staff will inform the participant about their randomly assigned treatment delivery arm.

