### **8.3 Treatment Initiation**

Treatment initiation will occur after the baseline visit, within 12 weeks of enrollment, and as determined by the clinician. Prior to initiating treatment, the clinician must complete the provider checklist.

If treatment initiation does not begin within 12 weeks of enrollment, the participant will be withdrawn from the study.

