### **8.4 Chart Review Part 2**

Chart Review Part 2 should be completed at 12 weeks after enrollment regardless of if the participant initiates treatment. The following information should be collected:

- Pregnancy status
- Total bilirubin
- Albumin
- Prothrombin time
- HBV status
- HAV status
- Fibrosure, Fibroscan, liver biopsy (if available)
- Problem list diagnoses:
  - Cirrhosis
  - Psychiatric
  - Medical
- Imaging if advanced fibrosis/cirrhosis to rule out hepatocellular carcinoma (abdominal ultrasound/CT scan with contrast, or MRI with contrast)
- Reason why patient did not initiate treatment (if applicable)
- HCV Viral load
- HCV Genotype/subtype
- FIB-4 score
- Child-Pugh score
- ALT and AST levels
- Platelets
- HIV status
- HIV Viral load (if applicable)
- HIV CD4 count (if applicable)

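### SAP 4.1 treats Chart Review 2 as a baseline source, but the protocol completes it 12 weeks after enrolment, and no visible date rule keeps post-randomisation results out

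*SAP*

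**What the plan says.** SAP 4.1 gives CR2 two different dates. It is first an enrolment source ("the data at the screening (chart review 1), enrollment (Chart review 2), or baseline will serve as the primary data sources"). In the next sentence missing values are filled from it as a first-visit source: "they will be replaced by the secondary data such as the Visit 1/Baseline (chart review 2) research visit data". The section then sums up the time points of all baseline data as "screening, enrollment, and baseline/V1 visit (2 week period").

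The protocol dates it differently. Section 8.4 says "Chart Review Part 2 should be completed at 12 weeks after enrollment regardless of if the participant initiates treatment". The items on that form include the reason a patient did not start treatment, which can only be settled once the start window has closed. Section 8.2 says "The baseline visit should occur within two weeks of enrollment and prior to treatment initiation", and section 8.3 says "Treatment initiation will occur after the baseline visit, within 12 weeks of enrollment, and as determined by the clinician". Randomisation takes place at enrolment (Protocol 5.4 and 8.1.2).

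SAP Table 1 names CR2 as the only source for genotype, HIV co-infection, HIV viral load and HBV surface antigen. It is the secondary source, after Chart Review 1 (CR1), for cirrhosis and HCV viral load. The note under the table explains the codes for screening, enrolment, baseline and CR1, but not CR2.

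**The concern.** An analyst who takes SAP 4.1 at its word will believe that CR2 values come from the first two weeks and will see no reason to check test dates. A result obtained after assignment can then be stored as baseline and used in four places:

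- the baseline table;
- the imbalance screen at p<0.01;
- the adjusted mITT and per-protocol models (SAP 5.4);
- the clinical subgroups (SAP 6.1).

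The arm could influence such values even before the first dose. In the patient navigation (PN) arm the navigator's initial visit precedes treatment (Protocol 8.7.1), and navigator duties include scheduling HCV evaluations and arranging imaging and biopsy (Protocol Appendix One). Which results are in the chart by week 12 may therefore differ by arm. That bears on the Table 1 rows that report whether genotype, HIV or HBV data are available, as well as on the values.

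SAP 5.4 uses the screen to find imbalance created by unequal treatment initiation. A variable that assignment may itself have changed blurs that purpose. Adjusting for it, or forming subgroups on it, is no longer conditioning on a pre-randomisation characteristic.

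**Working it through.** The plan has no figure to reproduce here. The check is on dates and on where each variable goes.

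**1. Timing, counted from enrolment.** Randomisation is at week 0, the baseline visit by week 2, treatment start by week 12, and CR2 completion at week 12. CR2 therefore falls 12 − 2 = 10 weeks outside the two-week period that the SAP describes.

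Weeks since treatment start when CR2 is completed = 12 − start week:

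| Start week | Weeks since start at CR2 |
|---|---|
| 2 | 10 |
| 4 | 8 |
| 8 | 4 |
| 12 | 0 |

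A participant who has not started by week 12 is withdrawn (Protocol 8.3). Everyone in the mITT sample has therefore started, or is at the deadline, when the form is completed. These are form-completion dates, not specimen dates.

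**2. Where CR2 variables go.**

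| Table 1 item | CR2 role | Subgroup in SAP 6.1 | Main exposure |
|---|---|---|---|
| HIV viral load | only source | yes | value varies over time |
| HIV co-infection | only source | yes | availability; status largely stable |
| HBV surface antigen | only source | yes | availability; status largely stable |
| Genotype | only source | yes | availability; value largely stable |
| Cirrhosis | fallback | yes | rarely needed |
| HCV viral load | fallback | no | rarely needed |

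That is six characteristics, four with CR2 as sole source and two as fallback. CR2 feeds five of the ten clinical subgroup factors. All six can pass through the imbalance screen. Cirrhosis is in the model by default, unless removed for non-convergence.

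**3. Why the fallback is rarely needed.** Eligibility requires an HCV viral load test from any time, and AST, ALT and platelets within 12 months (Protocol 5.1). FIB-4 is calculated at enrolment (Protocol 7.1), and cirrhosis is a stratification factor (Protocol 5.4). A value from before randomisation should nearly always exist.

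**4. Genotype.** Screening under Protocol 8.1.1.a already collects "HCV genotype/subtype (ever"), so CR1 can hold a genotype from before randomisation. Table 1 does not use it.

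**5. Reach of the clearest case.** HIV viral load applies only to co-infected participants. With the planned 600 initiators, the protocol's 28% gives 0.28 × 600 = 168 people; the 20% example in SAP 6.3 gives 120.

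**The case against.** The strongest reply is that CR2 is a chart abstraction, so the date of the form is not the date of the test. Many of its items, such as bilirubin, albumin, prothrombin time and hepatitis status, look like pre-treatment work-up. The visit table in Protocol Appendix Three, as extracted, has a baseline chart entry for HIV viral load plus separate entries at weeks 4, 8 and 12, and Protocol 8.5.1 collects on-treatment values through those later reviews. This stands. The documents do not show that any CR2 value was measured on treatment. They show a wrong date label and no visible rule that would exclude such a value.

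Second, Table 1 carries footnote markers 15 to 19 on the cirrhosis, genotype, HCV viral load, HIV co-infection and HBV rows, and the footnote text is not in the copy available. A date limit may be stated there. This also stands as a caveat. The HIV viral load rows carry no marker of their own, and a footnote would not correct the timing given in the body of SAP 4.1.

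Third, a reader might infer that baseline HCV viral load is badly distorted because it falls sharply on treatment. The documents do not support that. CR1 is used first, the test is needed for eligibility, and no fill rate from CR2 is given. HCV viral load is not a listed subgroup either.

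Fourth, a cut-off at first dose would keep more data than one at randomisation, since up to 12 weeks of pre-treatment evaluation lie between. It would remove on-treatment values but not the influence of the arm on which tests are done before treatment. Randomisation is the safer limit for anything used in inference; later pre-dose results can still be described.

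**Conclusion.** The SAP and protocol contradict each other on when CR2 is done, and the SAP text available has no date limit to make the difference harmless. Post-randomisation results can therefore be recorded as baseline. HIV viral load is the main exposed variable. The availability rows for genotype, HIV and HBV come next. Cirrhosis and HCV viral load are marginal.

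A reader might go further and conclude that the SVR odds ratio between directly observed therapy and PN is biased. The documents do not establish this. Most CR2-only items are stable, HIV viral load concerns a minority, and a screened variable enters the mITT or per-protocol model only if it differs at p<0.01. The SVR model for the full intention-to-treat sample adds no screened covariates. The effect on the primary comparison cannot be computed from the documents and is probably small.

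The conclusion assumes that Protocol 8.4 describes actual practice and that the missing footnotes contain no date rule. If they do contain one, correcting the timing statement and the source order for genotype would remain. The point is still worth settling in the SAP, because the stated timing gives the analyst no prompt to filter by date.

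**What to change.** In SAP 4.1 and Table 1:

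1. Correct the timing of CR2 to agree with Protocol 8.4, and define the CR2 code in the table note.
2. Take genotype from CR1 first, with CR2 as fallback.
3. Accept time-fixed items from CR2: genotype, and HIV or HBV infection documented before randomisation.
4. For time-varying items used in the imbalance screen, as model covariates or as subgroups, use only results dated on or before randomisation and set later ones to missing.
5. Results dated after randomisation but before the first dose may be shown descriptively, labelled as such.
6. Report by arm how many CR2 values are dated after randomisation and how many after the first dose.

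This costs SAP wording and a date filter. Protocol 7.1 already has the dates of HCV-related tests reviewed; whether HIV and HBV test dates are captured needs confirming. The downside is some additional missing values, mainly for HIV viral load and HBV.
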